### 9.4.2

### Interim Analysis for Efficacy

Not planned.

### 9.4.3

### Interim Analysis for Futility

Not planned.

### 9.4.4

### Secondary Analyses

The ITT Population will be used in the primary analyses of all secondary outcomes. Similar ANCOVA methods to those described in the primary outcome analyses will be used to compare groups on each of the secondary outcomes. For any outcome measured at baseline, the corresponding ANCOVA will control for baseline value in addition to the covariates noted above. Because they are of secondary interest, tests on secondary outcomes will each be conducted at the two-sided 5% significance level without adjustments for multiple comparisons. All estimates of effect size will be accompanied by 95% confidence intervals. Data from all secondary outcomes will be presented regardless of extent of "significance".

Descriptive summaries of process data (attendance at intervention contacts, fidelity to intervention delivery, and acceptability of the Med-South dietary pattern) will be provided for participants randomized to the Med-South dietary pattern intervention group in the ITT Population. No inferential statistics (p-values or confidence intervals) will be presented.

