9.4.3 ANALYSIS OF THE SECONDARY ENDPOINT(S)

Analysis of Secondary Objectives (1-2)

The ITT Population will be used in the primary analysis of all secondary outcomes. Similar ANCOVA methods to those described above will be used to compare groups on each of the secondary outcomes; for any outcome measured at baseline, the corresponding ANCOVA will control for baseline value in addition to the covariates noted above. Blood pressure will be averaged over three repeated measurements at each visit. Because they are of secondary interest, tests on secondary outcomes will each be conducted at the 5% significance level with no adjustments for multiple comparisons. All estimates of effect size will be accompanied by 95% confidence intervals. Data from all secondary outcomes will be presented regardless of extent of “significance”. Descriptive summaries of process data (attendance at intervention contacts, fidelity to intervention delivery, and acceptability of the Med-style dietary pattern) will be provided for participants randomized to Group 1 in the ITT Population. No inferential statistics (p-values or confidence intervals) will be presented.

Analysis of Secondary Objective 3 (Economic Analysis)

We plan to conduct both a budgetary impact assessment and a cost-effectiveness analysis. The budgetary impact assessment will quantify the total and per participant costs of intervention delivery from the health system perspective using an Activity Based Costing (ABC) approach and cost tracking forms that the health economist ([name])¹⁵⁸⁻¹⁶⁰ has developed and refined in past behavioral trials. Using this approach, all relevant labor, materials and supplies, contracted services, and other relevant costs required to deliver the interventions will be captured by key activities. This information will allow policy makers to identify the total and per capita fixed and variable costs of the intervention and to forecast required budgets, should the intervention expand beyond the trial phase. The non-sunk cost estimates will also feed into the cost-effectiveness analysis.

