## **7.2 Key Secondary Outcomes**

Key secondary outcomes include changes in the following outcomes from baseline to 24 months.

- blood pressure
- A1c

- markers of inflammation
- skin carotenoids
- self-reported dietary patterns

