### 9.4.1

### Primary Efficacy Analyses

The primary analyses will be conducted using the ITT Population (i.e., all randomized participants) and will be repeated secondarily using the Per Protocol Population. We will compare the longitudinal mean % change in body weight between groups using analysis of covariance (ANCOVA), conducted using a linear mixed model. A mixed model will allow for the inclusion of all observed follow-up data for all participants. The model will include fixed effects for group, follow-up visit (4, 12, or 24 months), group-by-visit interactions, site (see operational definition as below), baseline weight, race/ethnicity, gender, and diabetes status. (When reviewing the analysis in May, 2025, we realize we inadvertently did not include age in the model. Our final models included age.) There is no plan to include other baseline variables (including those different) in the model. To account for within-participant correlation, the model will allow for correlated error terms using an unstructured covariance matrix. For the primary comparison, we will use a linear contrast (i.e., group -1 1 group\*follow-up visit 0 0 -1 0 0 1) of the model parameters to test for a treatment effect at 24-months at the 5% significance level. Secondarily, we will compare the groups at other time points and will estimate effect sizes along with 95% confidence intervals for each comparison. Additionally, we will expand the model by including appropriate interaction terms, one at a time, to examine the potential heterogeneity of intervention effect in sub-groups, including diagnosis (diabetes vs. no diabetes), race/ethnicity, sex (for gender, 2 participants not binary, so will for these will use sex as captured in the electronic health record), and by degree of baseline obesity ( $BMI \geq \text{median}$  vs. less). Interaction terms will be tested at the 5% significance level.

Next, we will use a longitudinal mixed effects logistic regression model to compare the groups for proportions losing  $\geq 5\%$  baseline body weight at each follow-up visit. Estimates of odds ratios and 95% confidence intervals will be provided. This model will control for the same covariates specified for the primary model and test the same interaction terms.

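### The secondary-outcome mixed models, read literally, share one baseline slope across the 4-, 12- and 24-month visits; if the slopes differ, this can cost precision at 24 months, and a baseline-by-visit term is a cheap safeguard

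*SAP*

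**What the plan says.** SAP 9.4.1 sets out the primary mixed model: "The model will include fixed effects for group, follow-up visit (4, 12, or 24 months), group-by-visit interactions, site", followed by baseline weight, race/ethnicity, gender and diabetes status as further fixed effects. A note of May 2025 adds age to the final models. The only term crossed with visit is group. For the residuals, "the model will allow for correlated error terms using an unstructured covariance matrix". Other interactions are mentioned only for subgroups: "we will expand the model by including appropriate interaction terms, one at a time, to examine the potential heterogeneity of intervention effect in sub-groups".

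SAP 9.4.4 carries this model over: "Similar ANCOVA methods to those described in the primary outcome analyses will be used to compare groups on each of the secondary outcomes". It then adds that, for any outcome with a baseline measurement, "the corresponding ANCOVA will control for baseline value in addition to the covariates noted above". Protocol 9.4.3 reads the same way: "Similar ANCOVA methods to those described above will be used to compare groups on each of the secondary outcomes".

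SAP 7.2 fixes the time point: "Key secondary outcomes include changes in the following outcomes from baseline to 24 months". The outcomes listed there are blood pressure, A1c, inflammation markers, skin carotenoids and self-reported diet.

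**The concern.** A baseline main effect in a three-visit model gives one slope for all visits. With an unstructured covariance, that slope is a weighted average of the visit-specific slopes, and visits with less residual variance tend to count more. If follow-up values track baseline closely at 4 months and more loosely at 24 months, the shared slope is too steep at 24 months, and the 24-month contrast is adjusted by the wrong amount for the chance baseline difference between arms.

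What is at stake is mainly precision, at the visit on which the key secondary outcomes are defined. A second possible consequence is bias when dropout depends on baseline, because a wrong 24-month slope then feeds into the model's handling of missing values. This reaches the treatment contrast only under a particular dropout pattern, examined below.

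**Working it through.** **1. The plan's own figure.** Protocol 9.2 and SAP 9.6 give a detectable effect size of 0.33 with N = 360, 20% attrition, 80% power and alpha 0.05.
- Per arm: 360 × 0.8 / 2 = 144.
- Effect size: (1.960 + 0.842) × √(2/144) = 0.330. This reproduces.
- Systolic BP: 0.330 × 23.1 = 7.63, against 7.6 in Protocol Table 5.

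These figures use the SD of change with no baseline adjustment, so they do not depend on which slope model is fitted.

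**2. Formula for the loss (large sample, complete data).** Let β be the vector of slopes of follow-up on baseline at 4, 12 and 24 months, S the follow-up covariance given baseline, and **1** a vector of ones.
- Shared slope: b = **1**ᵀS⁻¹β / **1**ᵀS⁻¹**1**.
- Variance of the 24-month contrast, shared slope relative to visit-specific slopes: 1 + (b − β₂₄)² / S₂₄,₂₄.
- With all SDs equal to 1, βₜ = rₜ (the correlation with baseline) and S₂₄,₂₄ = 1 − r₂₄².

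The ratio is never below 1, and it equals 1 when the slopes are equal.

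**3. One case in full.** Assume r = 0.70/0.60/0.50 and a between-visit correlation of 0.60.
- S has diagonal 0.51, 0.64, 0.75 and off-diagonals 0.18 (4 and 12 months), 0.25 (4 and 24) and 0.30 (12 and 24).
- The weights on the three slopes are 0.491, 0.333 and 0.175.
- b = 0.491 × 0.70 + 0.333 × 0.60 + 0.175 × 0.50 = 0.632.
- Ratio = 1 + (0.632 − 0.50)² / 0.75 = 1.023.

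**4. Range.** All correlations are assumptions. In each row the two figures are for between-visit correlations of 0.60 and 0.75. Power is Φ(2.802/√ratio − 1.960), for an effect that visit-specific slopes detect with 80% power.

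| r at 4/12/24 months | Variance ratio, equal SDs | Power, shared slope | Variance ratio, SDs 1.0/1.1/1.2 |
|---|---|---|---|
| 0.60/0.60/0.60 | 1.000, 1.000 | 80.0% | not compared |
| 0.60/0.55/0.50 | 1.004, 1.005 | 79.8% (at 1.005) | 1.000, 1.000 |
| 0.70/0.60/0.50 | 1.023, 1.031 | 79.1%, 78.8% | 1.006, 1.008 |
| 0.75/0.60/0.45 | 1.064, 1.100 | 77.5%, 76.2% | 1.029, 1.046 |

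The last column matters because a slope is the correlation times the ratio of follow-up SD to baseline SD. If SDs grow as correlations fall, the slopes differ less. For 0.70/0.60/0.50 with SDs 1.0/1.17/1.40, all three slopes are about 0.70 and the loss vanishes.

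**5. Check with missing data.** Simulations used N = 360, 20% missing at 24 months at random and 1,500 replicates, with between-visit correlations of 0.7, 0.6 and 0.7 (4-12, 4-24 and 12-24 months). For 0.70/0.60/0.50 the SE ratio was 1.010 (empirical) and 1.014 (model-based). The formula gives 1.012 for that setting. Both estimators were unbiased.

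**6. Bias when dropout depends on baseline.** Simulations used N = 360, about 20% dropout and no true effect. Results are bias in the 24-month contrast, in SD units, under the shared slope.

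| Dropout-baseline relation | 0.70/0.60/0.50 | 0.75/0.60/0.45 |
|---|---|---|
| Same in both arms | none | none |
| In one arm only (log-odds 1 per SD) | 0.02 | 0.05 |
| Opposite in the two arms | 0.05 | 0.09 |

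Visit-specific slopes gave 0.00 to 0.01 in absolute value in the one-arm setting and about 0 in the opposite setting.

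**7. Cost of the extra term.** Two further slopes per outcome. The cost of estimating one slope is at most about √(1 + 1/288) − 1 = 0.17% of the SE.

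**The case against.** The strongest reply is that this is a preference about efficiency and not an error. Much of it stands.

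- **The loss is conditional.** A reader might infer that the model as written necessarily widens the 24-month contrasts. The documents do not support that. They give no baseline-to-follow-up correlations and no follow-up SDs, and the loss is zero if slopes are equal. For mild to moderate decay it is about 1.5% of the SE or less (√1.031 = 1.015).
- **Planned power is untouched.** A reader might infer that the stated detectable differences are too optimistic. They are not affected. Under 0.70/0.60/0.50, with the between-visit correlations of step 5, the shared-slope model detects a systolic BP difference of 6.68, against 6.61 with visit-specific slopes. Both are better than the planned 7.6.
- **Bias needs a specific pattern.** A reader might infer that baseline-related dropout alone biases the treatment contrast. With the same relation in both arms it does not; only the arm means shift. SAP 6.6 says some dropout may be related to the weight outcome, and the arms differ in contact intensity, so differential dropout is possible. Neither document shows it.
- **The wording leaves room.** Calling the methods similar does not expressly exclude a visit-specific baseline effect. That is a reason to state the term, since the literal list in SAP 9.4.1 omits it.
- **Timing.** SAP 6.4 carries an amendment of April 2025, and SAP 9.4.1 a note of May 2025 on reviewing the analysis and adding age. Another model change at that stage has a cost in credibility, most of all for the primary outcome.

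What remains on the other side is that the loss can only be zero or positive, the safeguard costs almost nothing, and the affected visit is the one that defines the key secondary outcomes.

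**Conclusion.** The point holds in a limited, conditional form. Read literally, SAP 9.4.1 and 9.4.4 give the secondary-outcome models one baseline slope for all three visits. If the true slopes differ, the 24-month contrasts can lose precision that visit-specific slopes would keep.

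With equal SDs and the assumed correlations, the extra variance runs from zero (equal slopes) through about 0.5% and 2-3% to about 6-10% in the steepest case tabulated. It is smaller in these falling-correlation cases if SDs grow over follow-up. Extra variance translates directly into equivalent sample size. Bias in the contrast arises only if the dropout-baseline relation differs by arm.

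The case does not extend to the primary model. Percent weight change is expected to depend only weakly on baseline weight, so little gain is likely there. This is a minor improvement, and its size rests on slopes that the documents do not give.

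**What to change.** In SAP 9.4.4, add outcome baseline by follow-up visit to the fixed effects of the secondary mixed models, and leave the 24-month group contrast unchanged. The cost is one line of text and two parameters per outcome, at most about 0.2% of the SE.

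Leave the primary model in SAP 9.4.1 as it is. If baseline weight by visit is wanted there, add it only as a sensitivity analysis.

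Date the change. If outcomes have already been analysed, label it post hoc or report it as a sensitivity analysis beside the model as written.

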## **9.5 Safety and Tolerability Analyses**

Prior to analysis, any data-captured adverse events will be coded by the principal investigators. Each type of event (by seriousness, severity, relationship to study) will be descriptively summarized in frequency tables by group (including only a single occurrence of any distinct type of event for any participant). The number of CVD events, ER visits, and hospitalizations will also be descriptively summarized by group. No inferential statistics (p-values or confidence intervals) are planned for comparing safety data between groups.

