6.3 MEASURES TO MINIMIZE BIAS: RANDOMIZATION AND BLINDING

Randomization

This is an open-label, randomized controlled trial of 360 participants desiring weight loss and followed over 24 months. Participants will be randomized 1:1, stratified by practice and diabetes status, to either:

- Group 1: Med-South Weight Loss Program (the intervention);
- Group 2: WW™ (Augmented usual care).

Randomized assignment will be done by using the randomization function in REDCap stratifying on site and diabetes status and using randomly permuted blocks of random sizes for the randomization to achieve balance in the participant allocation.

Unblinding Plan

As an open-label study, participants, providers, and many study staff will know to which group individual participants have been randomized. The investigative team, MPIs and Co-Is, (excluding the study statisticians [name] and [name]) will be blinded to group assignment of any

aggregated outcome data available before the completion of all data collection. Drs. [name] and [name] will not be blinded to study groups as their reports prepared for the DSMC will include unblinded data. Any key decisions by the study investigators (excluding the biostatisticians) regarding study outcomes, the appropriateness of test statistics or model assumptions, changes to this analysis plan, or any other statistical issues will be made in a masked review of the data (i.e., masked to the true randomization groups).

A randomization table (using randomly permuted blocks of random sizes for the randomization to achieve balance in the participant's allocation) will be prepared by the study statistician. This will be updated to the REDCap system by Drs. [name]. Only study biostatisticians will have access to this table. Outcome datasets provided to the statistician by the data management team will include the randomized arm assignment. Other study investigators will not have access to the primary outcome data until all data have been collected.

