7.2 PARTICIPANT DISCONTINUATION/WITHDRAWAL FROM THE STUDY

Participants are free to withdraw from participation in the study at any time upon request.

Participants will be withdrawn according to protocol for the following reasons:

- New diagnosis of condition on study entry exclusion criteria list (type 1 diabetes and cancer, as defined on the list).
- Other medical diagnosis typically associated with significant weight loss (5% or more of body weight). In addition to malignancy, examples include nonmalignant gastrointestinal disease, endocrinopathies, infectious disease, rheumatologic diseases, etc. As [name] (study Co-I, general internist) will be blinded to participants' study group assignment, he will adjudicate in these situations, seeking consultation from medical colleagues as appropriate.
- New diagnosis of cognitive decline confirmed by PCP as sufficient to interfere with insight related to food selection.
- New diagnosis of medical condition such that participation in a behavioral weight loss intervention is no longer appropriate.
- Permanent change in living situation (e.g. from home to nursing home) such that the participant has limited food options.

Pregnancy: Study participants who become pregnant may continue to participate in the study with the understanding that weight loss goals will be suspended during pregnancy through 3 months postpartum. If a pregnant participant wishes to continue with counseling session during pregnancy, the focus on counseling will be on dietary quality. The participant may resume full participation 3 months postpartum. Any data collected while the participant is pregnant will be censored and follow-up data will not be collected until the participant is 6 months postpartum.

A participant will be considered lost to follow-up if we are unable to contact him/her according to this algorithm.

- Attempts at telephone contact:

- We will call up to 5 times over a 2 week period. We will attempt 2 calls during regular work hours (8:30 to 5:30 on weekdays) and 3 after hours, including Mon-Thurs evening between 5:31 and 9:00 pm and on Saturday calling between 8:30 and 5:30 pm.
- We will leave up to 2 phone messages.
- If no contact is made over this initial 2 week period as outlined above, we will undertake more limited contact attempts for an additional 2 weeks including up to 2 phone calls per week, 1 during business and the other during evening hours or on the weekend.

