9.4.4 SAFETY ANALYSES

Prior to analysis, any data-captured adverse events will be coded by the principal investigators. Each type of event (by seriousness, severity, relationship to study) will be descriptively summarized in frequency tables by group (including only a single occurrence of any distinct type of event for any participant). Number of CVD events, ER visits, and hospitalizations will also be descriptively summarized by group. No inferential statistics (p-values or confidence intervals) are planned for comparing safety data between groups.

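### The principal investigators code adverse events for the by-arm safety tables, and nothing masks the coders to the individual participant's arm

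*SAP*

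**What the plan says.** Protocol 9.4.4 states: "Prior to analysis, any data-captured adverse events will be coded by the principal investigators". SAP 9.5 repeats this ("any data-captured adverse events will be coded by the principal investigators") and describes the output: "Each type of event (by seriousness, severity, relationship to study) will be descriptively summarized in frequency tables by group". A participant counts once for each distinct type of event. The comparison is by eye: "No inferential statistics (p-values or confidence intervals) are planned for comparing safety data between groups".

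On masking, Protocol 6.3 says that "participants, providers, and many study staff will know to which group individual participants have been randomized". The principal investigators and co-investigators are blinded to the group assignment of "aggregated outcome data available before the completion of all data collection".

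An earlier step also bears on this. Under Protocol 8.3.3.2 and 8.3.4, a study clinician assesses severity and relationship when an event is recorded. Protocol 10.1.6 (the monitoring committee charter) has the principal investigators complete a report for each reportable event and lists them as committee members.

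Protocol 7.2 handles one related judgement differently. For withdrawals because of an illness that typically causes weight loss, a co-investigator is kept blind to participants' "study group assignment, he will adjudicate in these situations".

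**The concern.** Some of what is coded is judgement. Protocol 8.3.3.1 separates mild, moderate and severe by how far an event interferes with daily life and what treatment it needs. Event type leaves room too, since the list in Protocol 8.3.4 has residual categories. Type also drives the counts: because each distinct type counts once per participant, two infections coded to one category add one to the table, and coded to two categories add two.

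The coders lead the group whose own earlier programme was refined into the Med-South arm (Protocol 6.1.1). If they know the arm while coding, similar events could be graded or classified differently between arms. With no p-values or confidence intervals, a reader judges harm from the counts alone. In a study described as minimal risk (Protocol 8.2), severe events are likely to be few, so a small number of coding calls could alter the picture.

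**Working it through.** No formula applies, and the plan states no figure to reproduce. The check is whether any clause masks the coders to the individual's arm.

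**Step 1. Masking by task.**

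| Task | Place | Done by | Masked to the individual's arm? |
|---|---|---|---|
| Severity and relationship when an event is recorded | Protocol 8.3.3.2, 8.3.4 | Study clinician | Not stated |
| Individual event reports | Protocol 10.1.6 | Principal investigators | Not stated |
| Coding for the safety tables | SAP 9.5, Protocol 9.4.4 | Principal investigators | Not stated |
| Illness withdrawals | Protocol 7.2 | One co-investigator | Yes |
| Entry of follow-up weights from a photo | SAP 9.2, Table 4 | Study staff | Yes |

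**Step 2. Clauses that might fill the gap.**

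- The investigator blinding in Protocol 6.3 concerns aggregated outcome data before data collection ends. Coding works on individual events, so it is not covered.
- The masked-review sentence in Protocol 6.3 covers key decisions on study outcomes, tests, model assumptions, changes to the plan and other statistical issues. It does not name event coding. SAP Table 1 lists adverse outcomes among the secondary measures, so a generous reader could stretch the sentence that far, but its words do not do so.
- The dummy group variable in SAP 6.1 applies to the analysis of the primary outcome.

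None of the three masks the coders.

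**Step 3. Can the arm reach the coders?** The principal investigators write individual event reports and sit on the monitoring committee, and Protocol 6.3 says the reports to that committee contain unblinded data. Unsolicited events may surface at counselling visits (Protocol 8.3.4). Study staff counsel only the Med-South arm, so an event's source can disclose the arm.

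**Step 4. Where is there room for differential grading?**

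- Seriousness follows listed criteria (Protocol 8.3.2).
- Most solicited events are concrete diagnoses checked against the health record (Protocol 8.3.4).
- CVD events, emergency visits and hospitalisations are tabulated separately (SAP 9.5) and do not depend on a severity grade.
- What remains for the coding step is mainly severity and event type. Relationship is also judgement, but it is first graded by the study clinician.

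**The case against.** The strongest reply is that coding may be only clerical. Severity and relationship are recorded by a study clinician when the event occurs, and the later step might do no more than sort events into the fixed list. This stands in part: the documents do not show how much discretion the coding step carries. It does not close the gap, because the clinician's grading is not stated to be masked either.

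Second, masked grading of relationship fits poorly with the protocol's own scale. Protocol 8.3.3.2 grades relationship to study procedures, including the intervention, by timing and by response to withdrawal. Removing programme references removes part of what the grader needs. A second grade could also differ from the one already reported to the monitoring committee and the IRB. This stands, and relationship should not be regraded.

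Third, masking the principal investigators themselves would be largely nominal, given their reporting and committee roles. This stands and points to a different coder.

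Fourth, the comparison with Protocol 7.2 is loose: those withdrawals affect weight data, since follow-up then stops (Protocol 7.1), whereas the safety tables are descriptive. This also stands. Section 7.2 shows that a blinded assessor is available; it does not show that the plan has accepted masking for adverse events.

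A reader might infer that the principal investigators know every participant's arm, or that the tables are biased. The documents say neither; they only fail to mask. A reader might also infer that the harm is beyond repair. It is not: health records back the events, and study data are kept for at least 10 years (Protocol 10.1.9.2), so a masked recode from source remains possible.

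**Conclusion.** The gap is real in both documents. The coders of adverse events for the by-arm tables are not masked to the participant's arm, which leaves event type and severity open to differential grading, and the earlier clinician grading has the same weakness. The reach is modest: the safety tables are descriptive, and the primary endpoint is unaffected.

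The size cannot be derived from the documents. A reader might take 180 participants per arm (360 / 2), assume that 20 to 40% have an event and that 5 to 10% of calls shift in one arm, and obtain 180 x 0.20 x 0.05 = 1.8 to 180 x 0.40 x 0.10 = 7.2 participants. Neither rate has a source in the documents. The product also counts participants with any event, not the severe or related ones where an imbalance would matter, so it should not be read as an estimate.

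The conclusion rests on the absence of a masking statement and on coding having at least some discretion over type or severity. The change is cheap and worth making, but it does not bear on the validity of the efficacy result.

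**What to change.** In SAP 9.5 and Protocol 9.4.4, state that:

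1. event type and severity for the tables are coded from a listing with arm, counsellor and programme references removed, preferably by the co-investigator already blinded under Protocol 7.2;
2. that coding is locked before arm is merged;
3. the relationship grade recorded at the time of the event is the one reported, so that it agrees with the monitoring committee and IRB reports, and it was assigned without masking.

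Keep the clinician's original severity grade in the dataset and report how often the masked grade differs. SAP 9.4.1 mentions a review of the analysis in May 2025, so coding may already be finished. If it is, recode type and severity from a masked listing, or report that coding was not masked. Expedited reporting under Protocol 8.3.5 is unchanged.

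The cost is a few sentences in each document, the editing of the listing, and some of the blinded co-investigator's time. The downside is that masking is partial: some narratives will still reveal the programme.
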